#### **Serious Adverse Events:**

Serious Adverse Events/KCI USA, Inc. Reporting Information  
Notification of the event will occur via the KCI USA, Inc. SAE Report Form. This form should be completed by the investigator, or designee, and faxed to KCI USA, Inc. Initial notification of the event may occur via telephone call to a KCI study contact, but must always be followed by written notification using the SAE Report Form by the close of the next business day. The KCI USA, Inc. SAE fax line is available for SAE reporting 24 hours per day and is monitored during normal business hours.

KCI USA, INC. SAE REPORTING BY FAX

Investigation: Insert Protocol Name Here

[contact]

#### **Statistical Analysis:**

#### **Sample Size Calculation:**

- A. Event Rate Assumption(s): <5%
- B. Study Group (%): 100%
- C.  Comparator or  Sham Group (%): historic cohort from previous 3 years.
- D. Power Estimation:  95%  90%  85%  80% or Other – Specify: \_\_\_\_%
- E. Evaluable Rate Consideration: Specify: \_\_\_\_%
- F. Sample Size Calculation: 20 Total Number of Subjects. When population is not divided evenly, please specify how it will be divided and rationale for doing so:
- G. Interim Analysis - Sample Size Re-calculation:  Yes  No  Specify rationale:
- H. Number of Centers Projected: 1

This is an observational prospective study with no concurrent arm for comparison; we will use historic data from our center over the last 3 years to analyze results. The advantage of this approach is that there was no change in medical providers among trauma surgeons in the last 3 years. We also have a robust prospectively collected trauma registry that allows performing this analysis. We will identify patients who have undergone emergent abdominal surgery with hollow viscus violations, and had undergone wet-to-dry dressing changes. A Propensity matching analysis will be performed to match patients from the historic cohort to the current patients by demographics, disease severity and laboratory tests. A univariate analysis, independent t-test, and a Kaplan-Meier survival analysis will be performed to compare rate of infection, time-to-closure, and cost analysis.

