**PI: [name]**

**The University of Arizona**

**[name]**

**[name]**

**T: [contact]**

## Sample Size: 20 subjects

### Introduction:

Postoperative surgical site infection (SSI) remains a common and serious complication after emergency abdominal surgery with incidence varying between 14 to 32% (1, 2). Seamon et al in a study of 503 trauma patients who underwent laparotomies for *any* enteric injuries demonstrated that primary closure leads to a 3 fold increase in SSI rate (32.1% vs. 9.8%) and 3 fold increase in fascial dehiscence (8.6% vs. 2.6%) compared to wounds managed with delayed closure (3). In contrast, an individual undergoing major *elective* operation is expected to have a 2% risk of SSI (4). Among the various gastrointestinal sites, colorectal procedures are associated with the highest risk of SSI due to the change in bacterial flora from largely aerobic gram-positive organisms in the proximal bowel to more virulent anaerobic species in the colon and rectum such as *Escherichia coli*, *Streptococcus*, *Bacteroides fragilis*, *Proteus* and *Klebsiella* (5-8). In a prospective cohort study of 2393 patients undergoing elective colorectal surgeries, Huebner et al. has shown hospital SSI rates varying between 4% to 25.2% and individual surgeon rates varying from 3.7 to 36.1% (9-14). The most feared consequence of SSI is fascial dehiscence and necrotizing soft tissue infections, which can lead to some of the most difficult surgical complications such as large ventral hernias or enterocutaneous fistulas (15-17).

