Over the years, various techniques have been employed to decrease SSI after bowel surgeries, particularly in emergent cases with significant enteric contamination. They include wet –to-dry dressing changes followed by delayed primary closure; wet-to-dry for several days, followed by VAC; or take a chance with infection with primary closure. Unfortunately, in the current age of medical practice treatment of the abdominal wound after emergent surgeries with enteric contamination is still largely “surgeon preference.” Among the previously mentioned techniques, most employ some form of wet-to-dry dressing change (18-19). A systematic review of 8 clinical trials encompassing 623 patients with contaminated abdominal wounds randomized to wet-to-dry dressings or delayed primary closure did not provide definitive evidence that there is advantage of one over the other in reducing surgical site infections (20). Either method involves the patient having an open wound for some time that is resource intensive and costly to manage, not to mention traumatic for the patient (21).

The VAC has revolutionized the management of complicated wounds. It operates on the principles of applying constant negative pressure therapy to a wound bed through a porous sponge to stimulate local blood flow, decrease interstitial edema and remove harmful enzymes in order to promote healing (22-25). However, the immediate application of the VAC after emergent highly contaminated operations has not been studied. Anecdotally, surgeons are reluctant to immediately use the VAC because theoretically the local environment after VAC closure is similar to primary closure. Some surgeons, however, will use the VAC after an initial 3 to 4 days of wet-to-dry, when the wound is heavily infiltrated with host neutrophil activity. This is a common approach at our institution. However, patients without insurance coverage cannot benefit from this technique, and often have to resort to the cumbersome and painful wet-to-dry dressing changes. A technique utilizing existing technology that can achieve definitive wound closure before the patient is discharged home is desperately needed. The VeraFlo, we believe, is that solution.

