### **Recruitment Methods and Consenting Process:**

The attending trauma surgeon will identify eligible patients for the prospective cohort. Recruitment and consent will happen in person with a thorough explanation of the treatment protocol by the PI, trauma surgeons, research coordinator or a research fellow. Patients or their Legal Authorized Representatives (LAR) will be informed about the study and consented. Should the patient or the LAR decline participation in the study, immediate cessation of data collection will take place and their information will not be included in the final data analysis.

Retrospective cohort of patients will be identified through medical chart review and we request waiver of consent for this patient population under 45 CFR 46.116(d) and 21 CFR 50.55 (d) as this retrospective research involves no more than minimal risk to subjects, doesn't alter the treatment or management in anyway as it had

already been completed, and it could not practicably be carried out without the waiver as those patients have completed their treatment and it would be extremely hard to obtain consent.

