### **Procedures Involved in the Human Research:**

We will approach patients upon the diagnosis to consent them for this prospective study. During the process, the details of the trial will be reviewed along with potential risks and benefits, the endpoints of interest and the process by which these endpoints are evaluated. When notified of trial enrollment, the patient or their legal representative will be given the opportunity to withdraw from further data and sample collection. Those who consent will be enrolled to collect data on outcomes, baseline parameters and follow-up period to evaluate efficacy of VeraFlo for management of contaminated abdominal wounds after emergent surgery. VAC with 1/4% Dakin's solution will be placed immediately at the end of the surgery for the first 3 postoperative days, followed by delayed primary closure on postoperative day 4. Wound will be swabbed at the end of surgery before placing the VAC and before skin closure on Day 4. All follow-ups will be performed as a standard of care.

Data collected will include the following: demographics (i.e. BMI), hemodynamic parameters at the time of presentation and operation, source of infection, imaging studies outcomes, lab tests, surgical procedure performed and its duration, vasopressors, estimated blood loss and transfusion records, antibiotics used and duration, comorbidities (Charlson Morbidity Index, APACHE II), trauma registry data, and complications (if any) during their hospital stay and follow-up in clinic, length of stay (in ICU and in hospital), intra-abdominal wound culture, wound closure details, pain level, cost, wound appearance (recorded by photograph), wound culture, infection, time of nursing care.

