#### **Information Management:**

We will not be distributing specimens to collaborating entities. The subjects will be identified by a study number only. All hard copy source documentation will be kept in a secured, locked cabinet in the site's research coordinator's office. All study documents will be maintained in a secure location per university policy, currently six years after conclusion of study. The following data will be collected from each patient: demographics (i.e. BMI), hemodynamic status at the time of presentation and operation, procedure performed and its duration, vasopressors, estimated blood loss and transfusion records, antibiotics used and duration, comorbidities (Charlson score, APACHE II), complications (if any), length of stay (in ICU and in hospital), intra-abdominal wound culture, wound closure details, pain level, cost, wound appearance (recorded by photograph), wound culture, infection, time of nursing care.

The electronic data will be entered and maintained on password protected computers stored in the investigator's office. All the data will be destroyed following the minimum 6 year requirement period by shredding any remaining documents and/or deleting computer files with linking information so there is no direct link to subject identifiers and information.

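### An unchanged surgeon roster does not balance surgeon mix between the VeraFlo and historical cohorts, and the operating surgeon is neither a matching variable nor a named data field

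*Combined protocol and SAP*

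**What the plan says.** The study is single-arm, with a historical wet-to-dry cohort as comparator. Under Statistical Analysis, Sample Size Calculation, the plan gives this in favour of that comparator: "The advantage of this approach is that there was no change in medical providers among trauma surgeons in the last 3 years". Propensity matching will then "match patients from the historic cohort to the current patients by demographics, disease severity and laboratory tests". Surgeon is not in that list.

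The two lists of data items (Procedures Involved in the Human Research; Information Management) include items such as "surgical procedure performed and its duration, vasopressors, estimated blood loss and transfusion records", but neither names the operating surgeon. The Data Collection Flow Sheet has no row for it. Subject Exclusion Criteria says the historical cohort will have the same data points, so the omission applies to both cohorts.

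Three other statements bear on the role of the surgeon:

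- Introduction: "treatment of the abdominal wound after emergent surgeries with enteric contamination is still largely" a matter of surgeon preference.
- Recruitment Methods and Consenting Process: "The attending trauma surgeon will identify eligible patients for the prospective cohort".
- Introduction, citing a cohort of elective colorectal operations: "individual surgeon rates varying from 3.7 to 36.1" per cent for SSI.

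**The concern.** A fixed roster means that the same people were operating. It says nothing about how the 20 VeraFlo patients and their matched controls divide among those people. A surgeon could supply many of one cohort and few of the other with no change in staffing.

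The plan's own text makes unequal shares plausible. Study Population expects about 90 suitable operations a year and 20 enrolments, so a few willing surgeons could supply the whole prospective cohort. Controls are limited to patients who had wet-to-dry dressings, a technique that the plan treats as chosen by the surgeon. Surgeon is thus plausibly linked to cohort membership and, on the plan's own citation, to the primary outcome, which makes it a potential confounder that the matching omits. At stake is whether a difference in SSI between cohorts can be read as a difference between wound treatments.

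**Working it through.** The plan gives no figure for surgeon imbalance, so there is nothing to reproduce. The check is how far surgeon mix alone could move the SSI comparison if the device had no effect.

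**Inputs from the plan**
- Surgeon-specific SSI, lowest and highest: 3.7% and 36.1% (Introduction; elective colorectal surgery, 2393 patients).
- Treated patients: 20. Event rate assumption: below 5% (Sample Size Calculation).
- Background SSI after emergency abdominal surgery: 14% to 32% (Introduction).

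**Assumptions, not in the plan**
- Two kinds of surgeon, low-rate (L) and high-rate (H), with no device effect.
- High-rate surgeons treat 20% of VeraFlo patients and 50% of controls.

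**Formula.** With w the share treated by high-rate surgeons, expected SSI = (1 − w) × L + w × H. The spurious difference (control minus VeraFlo) = (w_control − w_VeraFlo) × (H − L).

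**Cited extremes, L = 3.7%, H = 36.1%**
- VeraFlo: 0.8 × 3.7 + 0.2 × 36.1 = 2.96 + 7.22 = 10.18%.
- Control: 0.5 × 3.7 + 0.5 × 36.1 = 1.85 + 18.05 = 19.90%.
- Difference: 19.90 − 10.18 = 9.72 points. Each 10-point difference in share contributes 0.10 × 32.4 = 3.24 points.

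**Narrower spread, L = 10%, H = 20% (assumed)**
- VeraFlo: 0.8 × 10 + 0.2 × 20 = 12%.
- Control: 0.5 × 10 + 0.5 × 20 = 15%.
- Difference: 3 points.

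**Direction.** If the shares are exchanged, so that high-rate surgeons treat 50% of VeraFlo patients and 20% of controls, the same sums give −9.72 and −3 points. VeraFlo would look worse.

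**Effect on a significance test.** Exact enumeration of a two-sided Fisher test at 0.05 gives the chance of a result favouring VeraFlo with no device effect. The test, its level and the control numbers are assumptions, because the plan fixes none of them.

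| Expected SSI, VeraFlo vs control | 20 vs 20 | 20 vs 60 |
|---|---|---|
| 19.9% vs 19.9% (equal mix) | 1.1% | 1.2% |
| 10.2% vs 19.9% (cited extremes) | 6.8% | 8.6% |

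**Events available for adjustment.** 20 × 5% = 1, so about one infection or fewer is expected among the treated patients on the plan's own assumption.

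**The case against.** The strongest reply is that the plan calls the stable roster an advantage and no more, and that this is true: turnover is a real threat to a historical comparison. A reader might infer that the plan claims to have controlled operator differences. It does not say so. What can be said is that this is the advantage it names for the comparison, and that it covers less than it may appear to.

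A reader might also infer that a surgeon imbalance could never be detected. The documents do not support that either. Controls come from medical charts, trauma registry data are to be collected, and the operating surgeon would ordinarily be in the operative record. The accurate statement is that surgeon is not a named field and no use of it is planned.

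The selection mechanism is inferred. The protocol also describes round-the-clock research nurses and consent by several roles, and nothing shows that a few enthusiasts would supply most cases. It also describes wet-to-dry as the commonest technique, which weakens the argument that controls come from a distinctive group of surgeons. These points reduce the likely imbalance but do not show that shares would be equal.

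Finally, the 9.7 points rest on extremes from elective surgery and on assumed shares. A reader might set them beside the roughly 9-point gap between the assumed 5% and the 14% background rate (14 − 5 = 9) and conclude that surgeon mix would explain the expected benefit. That closeness comes from the inputs chosen and is not evidence.

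**Conclusion.** The concern holds as a gap in design and data collection. Roster stability does not balance surgeon mix, and the stated matching and data lists make no provision for it. The bias can go either way, and its size at this centre is unknown. Under the assumed 80%/50% shares it is 3 points with a 10% to 20% spread and 9.7 points with the cited extremes. The latter is an upper-end illustration for that split, not an estimate. With equal shares it is zero.

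The conclusion rests on surgeon affecting both SSI risk and cohort membership, which the plan's own statements make plausible but do not prove for this hospital. It does not depend on the sample-size figure. A correction is worth making because the remedy is cheap, and because the protocol expects the results to inform standard management of these wounds.

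**What to change.** 1. Extract a coded operating surgeon from the operative record in both cohorts, and add it to the data lists and the flow sheet.
2. Draw matched controls only from surgeons who enrolled at least one VeraFlo patient. This secures overlap but not equal shares: in the illustration above both kinds of surgeon enrol, so restriction alone would leave the imbalance. Where the pool allows, therefore, prefer a control from the same surgeon or surgeon group, with any grouping fixed without sight of SSI outcomes.
3. Report the surgeon distribution in both cohorts, and give the unrestricted match as a sensitivity analysis.
4. Replace the roster sentence with a statement that roster stability removes turnover but does not balance surgeon mix.

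The cost is one field per patient, a smaller control pool and somewhat coarser matching on demographics, severity and laboratory tests. A multi-level surgeon term in the propensity model and SSI rates by surgeon are not needed. With 20 treated patients and about one expected event, neither would be informative.

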### **Clinical Hypotheses:**

We hypothesize that immediately after emergent operations involving enteric injuries e.g. traumatic injuries involving stomach, small bowel, or colon; or the non-trauma emergent general surgical pathologies involving the above hollow viscera, the application of VeraFlo with 1/4% Dakin's solution for 3 days, followed by delayed primary closure on postoperative day 4, will be associated with a low risk of wound infection, achieve more expedient wound closure, ease nursing care and increase patient comfort compared to the current common practice of wet-to-dry dressing changes.

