#### **Superficial incisional SSI**

Must meet the following criteria:

Infection occurs within 30 days after any NHSN operative procedure (where day 1 = the procedure date), including those coded as 'OTH'\*

and

involves only skin and subcutaneous tissue of the incision

and

patient has at least one of the following:

- a. purulent drainage from the superficial incision.
- b. organisms isolated from an aseptically-obtained culture of fluid or tissue from the superficial incision.
- c. superficial incision that is deliberately opened by a surgeon, attending physician or other designee and is culture positive or not cultured

and

patient has at least one of the following signs or symptoms: pain or tenderness; localized swelling; redness; or heat. A culture negative finding does not meet this criterion.

- d. diagnosis of a superficial incisional SSI by the surgeon or attending physician or other designee .

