### **Subject Exclusion Criteria**

Prisoners

Age<18

Pregnancy

Patients with allergy to Dakin's (sodium hypochlorite) solution

Enrolled in a concurrent ongoing interventional, randomized clinical trial.

This prospectively collected cohort of patients will be compared to the similar historical cohort from 2008-2013. We will review medical charts of the patients admitted to UAMC following the same inclusion and exclusion criteria described above to perform a retrospective review. We will collect the same data points as in prospective cohort.

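### The rule for selecting historical controls does not require wet-to-dry dressings to have begun at the index operation, so a wound packed because of an SSI can qualify as a control

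*Combined protocol and SAP*

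**What the plan says.** The combined protocol and SAP describes a single prospective arm of 20 patients compared with historical patients from the same centre. Four parts bear on who becomes a control.

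- **Dressing criterion.** The Sample Size Calculation section takes patients who had emergent abdominal surgery with a hollow viscus breach "and had undergone wet-to-dry dressing changes". It gives neither a start time nor an indication for the dressings.
- **Other eligibility.** The Subject Exclusion Criteria section says that charts will be reviewed "following the same inclusion and exclusion criteria described above to perform a retrospective review". None of those criteria concerns how the skin was managed.
- **Matching.** Propensity matching is planned "to match patients from the historic cohort to the current patients by demographics, disease severity and laboratory tests". Initial skin closure is not among these factors.
- **Intended comparator.** The Clinical Hypotheses set VeraFlo with delayed closure on day 4 "compared to the current common practice of wet-to-dry dressing changes".

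The study treatment, by contrast, has a fixed start: the Procedures section places the device at the end of the operation. The Introduction lists several ways of handling these wounds, including "or take a chance with infection with primary closure", and says that "treatment of the abdominal wound after emergent surgeries with enteric contamination is still largely" a matter of surgeon preference.

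The primary outcome is superficial or deep incisional SSI by CDC definitions. One superficial criterion is a "superficial incision that is deliberately opened by a surgeon, attending physician or other designee and is culture positive or not cultured", with at least one local sign or symptom. The deep definition has a similar criterion.

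**The concern.** The two groups enter on different clocks. A VeraFlo patient is identified at the end of surgery, before any infection can occur. A control is identified by a treatment that may have started later and for a reason connected with the outcome.

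Consider a historical wound closed primarily. If it heals, the patient never has wet-to-dry dressings and is not a control. If it becomes infected, the surgeon may open it, which with symptoms can itself satisfy the SSI definition, and pack it. That patient now meets the dressing criterion and already carries the primary outcome. Packing after opening is a clinical assumption; the protocol does not describe it.

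Each patient who enters this way adds one SSI and no SSI-free patient, so the control rate moves in VeraFlo's favour. Matching on baseline characteristics cannot undo selection on a postoperative event, and a larger control pool only estimates the wrong rate more precisely. Time to complete closure, a secondary endpoint, is distorted too. These wounds were closed on the day of surgery and reopened later, so their closure time does not measure the same thing as that of a wound left open from the start.

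**Working it through.** **The plan's own figure.** There is none to reproduce on this point. The Sample Size Calculation section gives an event rate below 5% and a total of 20, but no control SSI rate.

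**Inputs**

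- d = 9.8%: SSI with delayed closure in the trauma laparotomy study cited in the Introduction. Used here for wounds packed from the index operation.
- p = 14% to 32.1%: SSI after primary closure. The upper value is the primary-closure rate in that same study. The lower value is the bottom of the 14% to 32% range that the Introduction gives for emergency abdominal surgery in general; using it for primary closure is an assumption.
- q = 10% to 25%: share of eligible historical patients closed primarily. Assumption.
- o = 50% to 100%: share of those patients' SSIs opened and packed wet-to-dry. Assumption.

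**Formula.** Per eligible historical patient, (1 − q) were packed from the start and q·p·o enter through an SSI. Therefore

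control rate = [(1 − q)·d + q·p·o] / [(1 − q) + q·p·o]

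If VeraFlo has the same true rate as wounds packed from the start, the apparent risk ratio is d / control rate.

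**Lowest case** (p = 14%, q = 10%, o = 50%): q·p·o = 0.0070. Rate = (0.0882 + 0.0070) / (0.9000 + 0.0070) = 0.0952 / 0.9070 = 10.5%. Risk ratio = 9.8 / 10.5 = 0.93.

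**Highest case** (p = 32.1%, q = 25%, o = 100%): q·p·o = 0.08025. Rate = (0.0735 + 0.08025) / (0.7500 + 0.08025) = 0.15375 / 0.83025 = 18.5%. Risk ratio = 9.8 / 18.5 = 0.53.

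| p | q | Control rate, o = 50% to 100% | Apparent risk ratio |
|---|---|---|---|
| 14% | 10% | 10.5% to 11.2% | 0.93 to 0.88 |
| 14% | 25% | 11.9% to 13.8% | 0.83 to 0.71 |
| 32.1% | 10% | 11.4% to 12.9% | 0.86 to 0.76 |
| 32.1% | 25% | 14.4% to 18.5% | 0.68 to 0.53 |

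With the index-operation requirement in place, q·p·o drops out and the rate returns to 9.8%, risk ratio 1.00.

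**Effect on a significance test.** The protocol states neither a matching ratio nor an exact test for the SSI rate. I took 20 versus 20 and a two-sided Fisher test at 0.05, by exact enumeration, with a true VeraFlo rate of 9.8%. The chance of a significant result favouring VeraFlo is 0.6% with equal rates and 5.8% in the highest case above. For scale, the standard error of the difference at 9.8% in both groups is √(2 × 0.098 × 0.902 / 20) = 9.4 percentage points, while the shift in the control rate is 0.7 to 8.7 points.

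**The case against.** The strongest reply is that the intended meaning is clear. The Introduction sets wet-to-dry and primary closure side by side as alternatives, the Clinical Hypotheses name wet-to-dry as current common practice, and the Potential Benefits section treats it as the most common technique for open abdominal wounds. A reader might infer that the protocol chose to admit patients packed at any time after surgery. It does not say so; that is only what follows if a rule without a time anchor is applied literally. This objection stands as to intent. It does not supply a rule, and a chart abstractor would work from the two sections that define controls. Wound closure details are a listed data item, but no selection step uses them.

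The second reply is that the size depends on unsupported inputs. This also stands. Nothing in the protocol gives the local share closed primarily. At q = 50% with p = 32.1%, the formula gives control rates of 22.3% to 31.7% and risk ratios of 0.44 to 0.31, but that share fits poorly with wet-to-dry as the most common technique, so I do not rely on it. The value o = 100% is an upper limit, since several SSI criteria do not require opening the wound and VAC is also used locally. A wound reopened and packed for a non-infectious reason would enter without an SSI, so late-packed wounds as a group may raise the rate less than modelled.

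Third, a reader might infer from the Subject Exclusion Criteria section that all primarily closed wounds become controls. Read with the dressing criterion in the Sample Size Calculation section, it does not admit them. Such an admission would in any case be confounding by closure method, a separate matter from entry that depends on the outcome.

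**Conclusion.** The concern holds as a gap in the control-selection rule. As written, the rule lets entry to the comparison group depend on the primary outcome. For every patient who enters because of an SSI the direction is certain: the control rate rises and VeraFlo looks better. Neither the eligibility criteria nor the matching factors correct this.

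The magnitude is not known. Over the assumed ranges above, a true control rate of 9.8% would be reported as about 10.5% to 18.5%. Those figures rest on rates from the Introduction, on assumed shares closed primarily and later packed, and on the assumption that opened wounds were packed wet-to-dry.

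It would go too far to conclude that the trial is likely to produce a false positive test. Within these ranges that probability stays at or below about 6% at 20 versus 20. The harm is mainly to the reported SSI rates and their difference, and to time to closure. It matters because the protocol proposes that less SSI and earlier closure could support standardising care. It should be corrected before the charts are abstracted.

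**What to change.** In both the Subject Exclusion Criteria and the Sample Size Calculation sections, define historical controls as patients whose skin was left open and whose wet-to-dry dressings began at the index operation, or at fascial closure if that was staged. Decide this from the operative note before SSI is abstracted. Exclude wounds that were closed primarily and opened later.

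The cost is one added selection rule within a chart review that is already planned. The 20 prospective patients are unaffected. Some historical controls will be lost. How many remain cannot be derived from the protocol, because the 276 patients counted under Study Population are not restricted to those treated with wet-to-dry dressings. The number meeting the new rule should be counted before the matching ratio is set.

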#### **Study Population:**

This is a prospective cohort study that will be performed at the University of Arizona Medical Center (UAMC), a Level I Trauma center. Patients who undergo emergent surgery for trauma induced enteric injuries

involving the stomach, small bowel, or colon (ex: gun-shot wounds, stab wounds, blunt colon perforation) or the non-traumatic emergent general surgical pathologies involving the above hollow viscera.

Retrospective review of our database over the past 3 years identified total of 276 patients: 157 patients underwent emergent surgery for trauma related colon injuries and 43 patients due to acute perforated diverticulitis. In addition, 76 patients underwent emergent abdominal surgery for perforated viscus excluding colonic pathologies. Based on these results, we conservatively estimate an average of 90 patients per year will require emergent abdominal surgery for perforated viscus. Thus, we anticipate **enrolling 20 patients** over the 1 year period. This will be followed by data collection, follow-up period, data analysis and report/manuscript about research findings.

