### **Subject Inclusion Criteria:**

Patients 18 years and older

Emergent surgeries involving enteric injuries e.g. traumatic injuries involving stomach, small bowel, or colon; or the non-trauma emergent general surgical pathologies involving the above hollow viscera.

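### The propensity match does not name bowel site, although the protocol ranks colorectal procedures highest for SSI and both cohorts mix colonic and non-colonic cases

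*Combined protocol and SAP*

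**What the plan says.** The protocol describes a single prospective arm of 20 VeraFlo patients compared with historical wet-to-dry controls. The subsection Sample Size Calculation, under Statistical Analysis, says propensity matching will "match patients from the historic cohort to the current patients by demographics, disease severity and laboratory tests". It continues: "A univariate analysis, independent t-test, and a Kaplan-Meier survival analysis will be performed to compare rate of infection", together with time to closure and cost. Neither sentence mentions bowel site, and no stratified or adjusted comparison is described.

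Other sections bear on whether site matters:

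- Introduction: "Among the various gastrointestinal sites, colorectal procedures are associated with the highest risk of SSI", which the text attributes to the change in bacterial flora along the bowel.
- Subject Inclusion Criteria: "traumatic injuries involving stomach, small bowel, or colon" are eligible, as are non-traumatic emergencies of the same organs.
- Subject Exclusion Criteria: the historical cohort is assembled "following the same inclusion and exclusion criteria described above to perform a retrospective review", and "We will collect the same data points as in prospective cohort".
- Study Population: in the three-year database review, "157 patients underwent emergent surgery for trauma related colon injuries and 43 patients due to acute perforated diverticulitis", and a further "76 patients underwent emergent abdominal surgery for perforated viscus excluding colonic pathologies".

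**The concern.** Treatment is not randomised, so the comparison depends on the match to make the groups alike on factors that drive SSI, the primary outcome. The protocol identifies one such factor itself and leaves it off the matching list. Shared eligibility criteria do not help, because every site is admitted in both cohorts. Disease severity does not ordinarily mean anatomical site. The severity and comorbidity measures the protocol names (APACHE II, Charlson, Injury Severity Score) are not described as recording it, so two equally ill patients may have a gastric and a colonic perforation.

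If the VeraFlo group held fewer colon cases than its matched controls, part of a lower SSI rate would be case mix read as a treatment effect. With more colon cases, a real benefit would be understated. The section on potential benefits says a favourable result may help to standardise management, so a reader will want to know whether the colon shares were similar. The plan neither secures that nor reports it.

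**Working it through.** The plan states no figure for this point, so the check measures how far an imbalance in site could move the result.

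**Step 1. Case mix (Study Population).** Colonic: 157 + 43 = 200. Total: 200 + 76 = 276, which agrees with the stated total. Colon share: 200/276 = 72.5%. Non-colonic share: 76/276 = 27.5%. Among 20 patients, 20 × 0.275 = 5.5 would be expected to be non-colonic. The review is not restricted to patients treated wet-to-dry, so this share stands in for that of the control pool.

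**Step 2. Shift from an imbalance.** With a common treatment effect,

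shift in SSI difference = (difference in colon share) × (colonic SSI rate − non-colonic SSI rate).

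No site-specific SSI rates are given. I assume gaps of 5, 10 and 18 points; 18 is the full width of the 14% to 32% incidence range in the Introduction (32 − 14). For a 20-point imbalance in colon share:

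| Assumed gap | Shift |
|---|---|
| 5 points | 0.20 × 5 = 1.0 point |
| 10 points | 0.20 × 10 = 2.0 points |
| 18 points | 0.20 × 18 = 3.6 points |

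**Step 3. Precision of the comparison.** Take 5% for VeraFlo (the upper limit of the event-rate assumption, which is below 5%) and 14% or 32% for controls. The matching ratio is not stated, so 1:1 and 1:2 are assumed. The formula is SE = √[0.05 × 0.95/20 + p(1 − p)/n].

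| Controls (n) | p = 14% | p = 32% |
|---|---|---|
| 20 | 9.2 points | 11.5 points |
| 40 | 7.3 points | 8.8 points |

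The largest shift is 3.6/11.5 = 31% to 3.6/7.3 = 49% of the standard error. With a 5-point gap the ratio is 1.0/11.5 = 9% to 1.0/7.3 = 14%.

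**Step 4. How often a 20-point imbalance would arise by chance.** Suppose both groups are independent draws from a population that is 200/276 colonic. The probability that the colon shares differ by at least 20 points is 21.4% for 20 versus 20 and 12.5% for 20 versus 40. The standard deviation of the imbalance is √[0.725 × 0.275 × (1/20 + 1/n)], which is 14.1 points (n = 20) or 12.2 points (n = 40). Multiplied by a gap of 5 to 18 points, that is 0.7 to 2.5 or 0.6 to 2.2 SSI points. This is sampling variation that matching on site would reduce. It does not show that the two cohorts truly differ.

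**The case against.** The strongest reply is that the matching list names categories only. APACHE II, Charlson and BMI are not spelled out there either, and trauma versus non-trauma, antibiotic use and operative duration are equally absent. On this view the real gap is the lack of a covariate list, and singling out site is a choice. Procedure and source of infection are to be collected, so a later list could include site. That is fair, but the documents contain no later list, and site is the factor the protocol itself ranks for SSI risk. Following the three stated categories would leave it out.

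Second, no bias has been shown. The centre, the trauma surgeons and the eligibility criteria are described as unchanged, and nothing in the documents says colon shares differ between periods. This stands, and it limits the claim to an unprotected comparison.

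Third, the magnitudes are soft. Chance imbalance in site is already contained in the binomial standard error, so the 31% to 49% ratio is added error only if the imbalance is systematic. Twenty points is also an attainable value at 20 versus 20: the chance of a difference strictly above it is 11.0%, not 21.4%. The Introduction's ranking concerns gastrointestinal procedures generally, not emergency contaminated laparotomy. The 72.5% share may not be that of the eligible population, since the review does not say where traumatic stomach and small-bowel injuries or non-diverticular colonic emergencies were counted. All of this stands and weakens the illustration. It leaves the omission itself untouched.

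**Conclusion.** The point holds, as a minor one. The stated match and the analyses after it leave unbalanced a factor that the protocol itself treats as prognostic for its primary outcome, in a non-randomised comparison where both cohorts admit every site.

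The effect is probably small beside the imprecision of a 20-patient study: 1.0 to 3.6 SSI points for a 20-point imbalance. That range rests on assumed site gaps, an assumed matching ratio and the database review's colon share. The direction cannot be predicted, and the figures show sensitivity to an imbalance; they do not estimate an actual bias. Confidence in the rating is medium.

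**What to change.** In the Statistical Analysis section, name bowel site (any colon involvement versus stomach or small bowel only) as a matching variable. Match exactly on it wherever a wet-to-dry control of the same site exists. Where none exists, keep the patient, match on the propensity score alone and report how often this happened. Report the standardised difference for site before and after matching. Exact matching adds no covariate to a score that 20 treated patients can barely support. Putting site into the score would also address the omission, at the price of one more term.

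The change takes one or two sentences. Site is not a named data field, so it must be abstracted from other records. The procedures section collects both source of infection and the operation performed, but the data list under Information Management keeps only the operation, which is therefore the safer basis. The same data points are promised for the historical cohort.

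The drawback is a smaller pool of eligible controls for each patient. At the database share, about 5 or 6 of the 20 patients would need non-colonic controls. The number of wet-to-dry controls by site is not given, so the feasibility of exact matching is untested. The fallback retains those patients, but some imbalance may persist where controls are scarce, which is why balance on site should be reported in any case.
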